This study measured change in the mean scores for three primary outcomes: contraceptive knowledge, effectiveness of most likely contraceptive method used in the next year, and accuracy of perceived pregnancy risk. We gathered baseline and follow-up measures for each of these outcomes immediately before and after the intervention, respectively.

Contraceptive knowledge was measured objectively using the 25-item Contraceptive Knowledge Assessment.¹ This produced a score between 0 (0% correct) and 25 (100% correct). Our contraceptive knowledge outcome was the change in this score between baseline and follow-up.

Effectiveness of most likely contraceptive method was operationalized using a woman's intention to continue using her current contraceptive method and the contraceptive method she reported being most likely to switch to were she to change methods in the next year. This measure was intended to be a realistic measure of the contraceptive method that women were most likely to use in the next year. We first asked women at both baseline and follow-up: "Do you intend to use the same birth control method(s) that you are currently using for the next year?" If the woman said she intended to keep her contraceptive method(s), the effectiveness of the most effective method she used in the past three months was used as her most likely method of contraception. The effectiveness of contraceptive methods was scored using the following WHO-defined categories²: IUDs, implants, and sterilization were considered highly effective (score = 3, 0-1% annual failure rate); the pill, patch, ring, and injection were considered effective (2, 2-9% annual failure rate); condoms, withdrawal, fertility tracking, and other methods were considered less effective (1, 10-30% annual failure rate); and no method

was its own category (0, 85% annual failure rate). If a woman said she did not intend to keep her current contraceptive method, we used the effectiveness of the most likely alternative contraceptive she would use. We measured this with the question, “If you had to change to a new birth control method in the next year, which of the following methods would you consider using?” Participants selected each method they would consider and then ranked the selected methods from most to least likely method. Our “effectiveness of most likely contraceptive method” outcome was the difference between a woman’s score at baseline and follow-up.

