pregnant or avoid pregnancy?”³ We measured past pregnancy scares by asking: “Have you ever had a pregnancy scare; that is, thought you were pregnant when you didn’t want to be, but later discovered that you weren’t pregnant after all?” We measured numeracy using the Berlin single item numeracy scale.⁴ This scale has been tested and validated to show that people who answer this question correctly are in the top 50% of the population in numeracy.⁴ Data were also collected on the sexes of the woman’s past sex partners, whether she had ever seen the poster before, and whether there were any types of birth control the woman could not use for health/safety or cost reasons. The following variables were measured using questions from the National Survey of Family Growth (NSFG): biological sex, age, whether the participant was trying to conceive or was currently pregnant, sexual intercourse in the past three months, education, time since first sex, and marital status. Finally, the following variables were measured using questions from the National Longitudinal Survey of Adolescent to Adult Health (Add Health): race/ethnicity (Wave V), income (Wave IV), relationship status (Wave IV), and health insurance type (Wave IV).

Analysis

We first tested whether the demographic and other factors were balanced between our randomized groups using two-sample t-tests and likelihood-ratio tests as appropriate. We did not find any statistically significant imbalances for any of the variables. We conducted two-sample t-tests on the change in the mean score for each of our outcomes to test whether each poster improved the three primary outcomes relative to baseline and in comparison to the other poster. We used the Bonferroni correction to account for multiple comparisons. Using the

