same methods, we also tested the hypothesis that the three pre-specified subgroups (low numeracy, pregnancy scares, and no birth control) had greater increases in their mean scores for the patient-centered poster versus the CDC poster. We chose these subgroups because the patient-centered poster was designed to appeal to the needs of these groups. Finally, because correct answers to some of the questions on the Contraceptive Knowledge Assessment were not given by either poster, we could determine the proportion of the change in contraceptive knowledge that was attributable to the posters. We did this by analyzing the change in contraceptive knowledge separately for questions that did and did not have the correct answer provided by either poster. All analyses were conducted in Stata (Stata/SE 15, College Station, TX, US).

For our power calculations, we assumed an alpha of 1% and a power of 80%. For our final analysis sample of N=936, comparing the two posters we can detect a 3 percentage point difference in mean change in contraceptive knowledge (standard deviation of 0.18¹), a 0.8 percentage point difference in accuracy of perceived pregnancy risk (standard deviation of 0.05), and a 6 percentage point difference in the mean change in effectiveness of most likely contraceptive method (standard deviation of 0.35⁵).

References

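### The detectable difference for method effectiveness is given in percentage points although the outcome is a change in a 0–3 tier score, and the stated inputs give about 0.08 in the SD's unit, not 0.06

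*Combined protocol and SAP*

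**What the plan says.** The Measures section scores the method a woman is most likely to use on four ordered tiers. At the top, "IUDs, implants, and sterilization were considered highly effective (score = 3, 0-1% annual failure rate"; at the bottom, using no method "was its own category (0, 85% annual failure rate". Tiers 2 and 1 lie between. The "outcome was the difference between a woman’s score at baseline and follow-up", so each woman contributes a whole number from −3 to +3. The only percentages attached to this score are the annual failure rates that describe the tiers. No rule turns the score, or a change in it, into a percentage.

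On the test, the Analysis section says: "We conducted two-sample t-tests on the change in the mean score for each of our outcomes". Its power paragraph states "we assumed an alpha of 1% and a power of 80" per cent, and continues: "For our final analysis sample of N=936, comparing the two posters". For this outcome the detectable effect is "a 6 percentage point difference in the mean change in effectiveness of most likely contraceptive method". The spread is given as "effectiveness of most likely contraceptive method (standard deviation of 0.35⁵", where the raised 5 is a reference number. The paragraph gives no unit for the SD and does not state sidedness or the allocation ratio.

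**The concern.** There are two faults in one clause.

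The first is the unit. Percentage points suit the other two primary outcomes: the knowledge score has a stated percent-correct equivalent (0 is 0%, 25 is 100%), and accuracy of perceived risk is scored 0 or 1. Method effectiveness has no such scale. A reader could take the 6 points as a share of women changing method or as points of annual failure rate, and neither is the outcome tested.

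The second is the number. Whatever the unit, 0.06 with an SD of 0.35 should follow from alpha, power and sample size, and it does not.

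At stake is the plan's statement of what it could detect on one of its three primary outcomes. As written, the statement credits the trial with more sensitivity than its inputs support, in a unit that cannot be set directly against the estimate.

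**Working it through.** **Inputs.** From the power paragraph: alpha 0.01, power 0.80, N=936, SD 0.35, stated difference 0.06. Assumed, because not stated: 1:1 allocation, so n = 468 per arm. Two-sided and one-sided tests are both shown.

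**1. Attempt to reproduce the stated 0.06.** For two means:

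MDD = SD × √(2/n) × (z_alpha + z_power), with √(2/468) = 0.06537.

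- Two-sided: 0.35 × 0.06537 × (2.576 + 0.842) = 0.0782.
- One-sided: 0.35 × 0.06537 × (2.326 + 0.842) = 0.0725.

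Neither rounds to 0.06. Unequal allocation makes it worse (0.0798 at 1.5:1, two-sided). Using N=990 or N=1000 instead of 936 gives 0.0760 or 0.0756.

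**2. Power at the stated difference.** The standard error is 0.35 × 0.06537 = 0.02288, and 0.06/0.02288 = 2.622.

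- Two-sided: Φ(2.622 − 2.576) = 0.519.
- One-sided: Φ(2.622 − 2.326) = 0.616.
- The noncentral t gives 0.517 two-sided, so the normal approximation is not the cause.
- If 6 is a rounded value, two-sided power runs from 43% at 0.055 to 60% at 0.065.

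**3. Sample size needed for 0.06 at 80% power, two-sided 1%.** 2 × (0.35/0.06)² × (2.576 + 0.842)² gives 795 per arm after rounding up, against 468.

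**4. Settings that would give 6 after rounding.**

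- 936 per arm, two-sided 1%: 0.0553. A one-sample test of change within one poster group of 468 has the same arithmetic.
- 468 per arm, one-sided 5%: 0.0569.
- 468 per arm, two-sided 5%: 0.0641. This fits the present outcome, but it gives 0.0092 for accuracy (SD 0.05), where the plan states 0.8 points.

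None of these matches the text, which gives alpha 1% and a comparison of two posters with 936 women in the final sample.

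**5. Does the unit change the power?** The difference and its SD must share a unit. Two readings keep them together:

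| Reading | Stated difference | SD | Difference/SD | Power, two-sided | MDD at 80% power |
|---|---|---|---|---|---|
| Both in tiers | 0.06 | 0.35 | 0.171 | 51.9% | 0.078 tiers |
| Both as a share of the 3-tier range | 0.18 | 1.05 | 0.171 | 51.9% | 0.235 tiers |

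The readings differ by a factor of three in tiers and not at all in power. In women per arm of 468, a net 0.06 × 468 = 28 more moving up one tier becomes 0.0782 × 468 = 37 on the tier reading.

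**The case against.** The strongest reply is that this is a labelling slip. The Measures section defines a 0–3 score and its change, the power paragraph mentions no rescaling, and 0.06 with an SD of 0.35 therefore reads naturally in tiers. The Analysis section is also written in the past tense about a final sample, so the sentence no longer sets the sample size, and a null result would be judged from the estimate and its interval. All of this stands, and it limits the weight of the unit fault. It does not answer the numerical fault, which is present on every scale.

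Three stronger readings are tempting, and the documents do not support them.

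- A reader might infer that the effect size is uncertain by a factor of three. The share-of-range reading rests only on analogy with knowledge, whose SD of 0.18 evidently puts a 0–25 score on a 0–1 scale. That makes it possible, not shown. A further origin cannot be excluded either: 0.35 is also about the SD of a yes/no variable at 14% (√(0.143 × 0.857) ≈ 0.35). The cited source is not available here to settle this.
- A reader might call an SD of 1.05 tiers impossible because it would need many women to jump two or three tiers. With mean change near 0 the variance is 1.05² = 1.1025. It could arise with 96.6% of women moving one tier and 3.4% moving two (0.966 + 4 × 0.034 = 1.102). The only firm floor on movement is that about 12% change tier at all (1.1025/9 = 0.1225).
- A reader might conclude from step 4 that the sponsor entered 936 as the size of each arm. That fits the stated figures for all three outcomes after rounding, but so does a one-sided 5% test, and the documents do not say which, if either, was used.

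**Conclusion.** The point holds in two parts. The percentage-point label is wrong for this outcome as defined. The stated figure is also too small for the stated inputs: the detectable difference is 0.078 in the SD's unit (two-sided) or 0.073 (one-sided), against 0.06, and power at 0.06 is about 52% or 62%, against the 80% claimed.

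This rests on 1:1 allocation and the normal approximation for two means; both sidedness options fail. It does not depend on whether 0.35 is in tiers or a share of the range. Expressing the result as 0.078 tiers does depend on the SD being in tiers. The randomisation, the outcome definition and the t-test are untouched. What is wrong is a stated design property of a primary outcome.

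**What to change.** In the power paragraph of the Analysis section, remove percentage points for this outcome and give both figures in tiers, along these lines: *with 468 women per poster, two-sided alpha 1% and 80% power, the detectable difference in mean change is about 0.08 tiers, assuming an SD of change of 0.35 tiers*. At 0.08 the two-sided power is 82%. State sidedness and allocation in the same sentence; if the intended test is one-sided, the figure is 0.073.

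Confirm from the cited source that 0.35 is an SD of change on the 0–3 scale. If it is not, name its scale and restate the difference to match (for a share of the range, 0.235 tiers with an SD of 1.05 tiers). Do not substitute an SD computed from this trial's own change scores, since that would turn a planning figure into post hoc power.

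The cost is one sentence and one look at a reference. The downside is that the detectable difference rises from 0.06 to about 0.08, so the statement is less favourable than the one now printed.
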